#### Randomization

The unit of randomization will be the nursing home, with all residents within a nursing home assigned to the same arm. Cluster randomization is the only feasible randomization method when an intervention must be applied (or is typically applied) to an entire group, such as a quality improvement initiative. It is also the only method for evaluating interventions for which individuals are linked, e.g., by shared exposure to contagious illness, as occurs in nursing homes. Cluster randomization also has the advantage of studying interventions under conditions of actual use, of minimizing disruption to normal practice, and of allowing the use of health system resources for ensuring compliance with the intended treatment.

[figure not shown]
In cluster-randomized trials, the relatively smaller number of randomized units means that simple randomization may not ensure balance of key variables by chance alone. The existence of *a priori* data allows us to improve balance through stratification. One way is to establish pairs with similar covariate profiles in which one member per pair is assigned to each arm. There is no "best" method of making pairs. One approach we used in

a prior trial is to calculate the Mahalanobis distance between facilities across all available key variables and choose the pairings with the minimum average within-pair distance. In this approach, we standardize the variables and then multiply by values calibrated to reflect any difference in their importance with respect to balance.

To select the best pairing scheme, we will compare this distance method to other pair construction schemes, using graphical methods to compare the balance between the arms under each scheme. For example, if two variables had to be balanced, we could tentatively divide the sample into two groups under a pair construction scheme and then generate a scatterplot showing the between-arm absolute value of the mean difference for one variable on the x-axis and the second on the y-axis for each possible result of the randomization. We would then divide the groups again under the same scheme, and find another point on the scatterplot. Repeating many times would show the typical distribution of balance under a scheme. Comparing the resulting scatterplots from each scheme can reveal the relative risks of imbalance and benefits for balance accruing to each scheme. One scheme may result in close balance on one key characteristic and very variable balance on the other, while a competing scheme may have good median balance on both characteristics, but a long tail implying a few bad-luck assignments with poor balance.

We aim to balance facility case mix based upon population age, wounds, comorbidities, and functional status scores, as well as infection prevention activities assessed by survey. To assess balance, we will use a parallel coordinates plot, a multivariate plot method. A simulation (**Figure**) shows a potential result of a single pair construction method using baseline values of volume, outcome, device use, and bathing frequency. Each blue, red, green, or black line shows the mean difference between arms for all four variables for one realized randomization under the scheme. The results show that a few randomizations, in blue, are relatively imbalanced on volume and outcome but are balanced on device use and bathing, while a few others, in black, have the reverse pattern. The green and red realizations are approximately equally balanced across these variables. If we considered it more important to balance on volume and outcome, this would not be an ideal scheme, as medium or poor balance is common.

**Figure. Parallel Coordinates Plot Showing Simulated Balance Across Multiple Variables**

## Statistical Analysis

All outcomes will be assessed similarly. Here, we use the example of the primary outcome: the probability a transfer to a hospital is for an infectious diagnosis. Main trial results will be based on as-randomized, unadjusted analyses using logistics regression models. Clustering within nursing home will be accounted for using random effects, which are added model terms that allow unique baseline rates for each nursing home, and are necessary to account for clustered randomization. Model terms will include individual-level data on arm, nursing home, outcome events, trial period (baseline vs. intervention) and an interaction term between trial period and arm. Trial success will be determined by the significance of the interaction term, which assesses whether the difference in log odds between the baseline and intervention period differs significantly between the two arms. We can write a simple version of the model symbolically as:

$$\text{logit}(\Pr[R_{ij}]) = \log\left(\frac{\Pr[R_{ij}]}{1 - \Pr[R_{ij}]}\right) = \beta_0 + \beta_1 \text{Arm}_{ij} + \beta_2 \text{Period}_{ij} + \beta_3 \text{Arm}_{ij} * \text{Period}_{ij} + b_i$$

where  $i$  is a nursing home,  $j$  is a resident within the nursing home, and  $R_{ij}=1$  if the transfer has an infection diagnosis and 0 if not.  $\text{Arm}$  and  $\text{Period}$  are indicator variables and are = 0 for patients in a nursing home in the control arm or baseline period and 1 if in the intervention arm or period, respectively. The random effect,  $b_i$ , allows for different readmission rates at each nursing home, and accounts for the clustering within a given nursing home. The ultimate effect of the intervention is assessed by  $\beta_3$ . If it is negative with p-value < .05 (or 95% CI excluding 0), then we can conclude that the intervention reduces the risk of infectious transfer.

Subsequent analyses will include as-treated and covariate-adjusted models. Adjusted models will account for individual age, gender, comorbidities (by diagnostic codes), and functional status scores. All analyses will use current versions of SAS (9.4), SAS/STAT (13.2, SAS Institute, Cary NC) and/or R (3.1.2).

## Power

We assessed power via resampling methods. We used preliminary data on outcomes adjusted to an 18-month baseline and intervention period. First, each nursing home was randomly assigned to a study arm. Then, individuals were sampled with replacement from within each nursing home to simulate “baseline” period data. Individuals were sampled again to simulate the “follow-up” period data. For nursing homes assigned to intervention arm, observed readmissions among the sampled follow-up individuals were removed at a given probability to reflect the effect of the intervention. Finally, the analysis planned for the trial was conducted on the resampled “baseline” and “follow-up” data. In this case, the planned analysis is a generalized linear mixed model logistic regression with main effects for period and arm, with the study effect assessed via their interaction, as described above. To estimate power, we repeated this process 200 times. The proportion of times that the null hypothesis of no interaction effect was rejected, with alpha = .05, provided the estimated power. In contrast to analytic approaches to power, we also needed to find confidence limits on the estimate, which we did using exact methods. For cluster-randomized trials, this approach has the advantage that it does not require guessing the value of the intra-class correlation coefficient, or, importantly, its variability. In addition, this approach does not require an assumption of constant cluster size.

For our primary outcome, preliminary data showed that 21.3% of hospital transfers from nursing homes were due to infection. For the probability of transfer due to infection, we assessed the power for a relative reduction of 15%, from 21.3% to 18.1%. Power was estimated at 89% (95% CI [83%, 93%]). For our key secondary outcome of the probability of transfer to a hospital among discharges, our preliminary data showed that 37.8% of discharges were associated with admission to hospitals across the nursing homes. For this outcome, we estimated the power for a relative reduction of 8%, from 37.8% to 34.8%, to be 99.5% (95% CI [97%, 99.9%]). Even at a relative reduction of 5%, we have 74% power (95% CI [67%, 80%]). These effect sizes are meaningful because there is tremendous

national interest in reducing preventable readmissions, of which infections are a major cause. Reductions in overall readmissions of 1-3% are lauded as sizeable in the CMS Hospital Readmissions Program which fined 2,225 hospitals in its first year, with each fraction of a percent resulting in substantial lost revenue. The second year of this program saw a reduction of 0.6% in all cause readmissions. In summary, our power assessment demonstrates adequate power to detect plausible and meaningful effects of the proposed trial.

#### Study Conditions and Period

Participating nursing homes (28) were randomized to

- **Arm 1 – Routine Care**

Nursing homes in this group arm did not change their bathing materials, timing, schedule, or other aspects of bathing regimen.

- **Arm 2 – Universal Decolonization**

Nursing homes in this group used chlorhexidine soap or wipes for admission bathing and then for all resident bathing. They did not otherwise change their bathing materials, timing, schedule, or other aspects of bathing regimen. In addition, nasal iodophor was administered twice daily Monday through Friday, every other week.

#### Study Periods

- 18-month baseline period: September 2015-February 2017
- Phase-in period: March-June 2017 (not included in analysis)
- 18-month intervention period: July 2017-December 2018

Note that the baseline period occurred before the beginning of trial activities, including randomization. Data collection for primary and secondary trial outcomes used electronic sources and could not have been affected by randomization status.

#### Trial Outcomes

| Trial Outcomes  | Explanation  |
|---|--|
| Primary outcome:
Hospital transfer due to infection, among hospital transfers | If the resident was transferred from the nursing home to a hospital, was the transfer made because the patient had an infection? |
| Secondary outcome:
Hospital transfer, among transfers                         | If the resident was transferred from the nursing home, were they transferred to a hospital?                                      |

Other outcomes are found in the below table. At the time of the study conception, these were planned for secondary manuscript submissions.

| Other Outcomes   | Explanation   |
|--|---|
| Multidrug-resistant organism (MDRO) colonization   | Was a resident colonized with a multidrug-resistant organisms (MDROs): (MRSA, VRE, ESBL, CRE)                               |
| Hospital transfer due to infection, among hospital transfers in Long Stay and Short Stay Subsets | As in above table, but with analyses stratified by length of stay.  |
| Hospital transfer, among transfers in Long Stay and Short Stay Subsets                           | As in above table, but with analyses stratified by length of stay.  |
| Emergency Department Transfer due to Infection; overall and in Long Stay and Short Stay Subsets  | Probability that a resident is sent to the emergency department for an infection, overall and stratified by length of stay. |

## Statistical Analysis

Main trial results will be based on as-randomized, unadjusted analyses using generalized linear mixed models logistic regression. All outcomes will be assessed similarly. Here, we use the example of the primary outcome: transfer to a hospital for an infectious diagnosis. Clustering within nursing home will be accounted for using random effects, which are added model terms that allow unique baseline rates for each nursing home, and are used to account for clustered randomization. Model terms will include individual-level data on arm, nursing home, outcome events, trial period (baseline vs. intervention) and an interaction term between trial period and arm. Trial results will be assessed through the interaction term, which measures the difference in log odds between the baseline and intervention period between the two arms. We can write a simple version of the model symbolically as:

$$\text{logit}(\Pr[R_{ij}]) = \log\left(\frac{\Pr[R_{ij}]}{1 - \Pr[R_{ij}]}\right) = \beta_0 + \beta_1 \text{Arm}_{ij} + \beta_2 \text{Period}_{ij} + \beta_3 \text{Arm}_{ij} * \text{Period}_{ij} + b_i$$

where  $i$  is a nursing home,  $j$  is a resident within the nursing home, and  $R_{ij}=1$  if the transfer has an infection diagnosis and 0 if not.  $\text{Arm}$  and  $\text{Period}$  are indicator variables and are = 0 for patients in a nursing home in the control arm or baseline period and 1 if in the intervention arm or period, respectively. The random effect,  $b_i$ , allows for different readmission rates at each nursing home, and accounts for the clustering within a given nursing home. The ultimate effect of the intervention is assessed by  $\beta_3$ . If it is negative with p-value < .05 (or 95% CI excluding 0), then we can conclude that the intervention reduces the risk of infectious transfer.

Subsequent analyses will include as-treated and covariate-adjusted models. Adjusted models will account for individual age, gender, comorbidities (by diagnostic codes), and functional status scores. All analyses will use current versions of SAS (9.4), SAS/STAT (13.2, SAS Institute, Cary NC) and/or R (3.1.2).

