## Power

We assessed power via resampling methods. We used preliminary data on outcomes adjusted to an 18-month baseline and intervention period. First, each nursing home was randomly assigned to a study arm. Then, individuals were sampled with replacement from within each nursing home to simulate “baseline” period data. Individuals were sampled again to simulate the “follow-up” period data. For nursing homes assigned to intervention arm, observed readmissions among the sampled follow-up individuals were removed at a given probability to reflect the effect of the intervention. Finally, the analysis planned for the trial was conducted on the resampled “baseline” and “follow-up” data. In this case, the planned analysis is a generalized linear mixed model logistic regression with main effects for period and arm, with the study effect assessed via their interaction, as described above. To estimate power, we repeated this process 200 times. The proportion of times that the null hypothesis of no interaction effect was rejected, with alpha = .05, provided the estimated power. In contrast to analytic approaches to power, we also needed to find confidence limits on the estimate, which we did using exact methods. For cluster-randomized trials, this approach has the advantage that it does not require guessing the value of the intra-class correlation coefficient, or, importantly, its variability. In addition, this approach does not require an assumption of constant cluster size.

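### The primary model has only a random intercept per nursing home, so the arm-by-period test assumes no home-to-home variation in change; any such variation makes the 5% test anti-conservative, and the stated 89% power leaves it out

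*Combined protocol and SAP*

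**What the plan says.** Both the original and the final statistical plan, under Statistical Analysis, fit a logistic mixed model with arm, period and their product. The final plan states: "Trial results will be assessed through the interaction term". Benefit is concluded if that coefficient, β3, is negative with p below .05.

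On clustering, the final plan says: "Clustering within nursing home will be accounted for using random effects, which are added model terms that allow unique baseline rates for each nursing home". The equation has one random term, b_i, indexed by home and not by period. It is introduced with "We can write a simple version of the model symbolically as", but no fuller version is written. Neither plan names a home-by-period effect, a random period slope, a robust variance, a permutation test or a small-sample degrees-of-freedom method. The final plan applies the same approach to all outcomes.

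Under Power, "individuals were sampled with replacement from within each nursing home to simulate" the baseline data. The same homes are then sampled again for follow-up, with events removed in the intervention arm to represent the effect. The planned model is fitted to the result.

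**The concern.** A home's random intercept is the same in both periods, so it drops out when that home's change is formed. What remains in the standard error of β3 is resident-level binomial error. Thousands of transfers then stand in for 28 randomised homes, and the test is valid only if every home in an arm has the same true change between two 18-month periods.

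There is reason to doubt that. The original plan justifies cluster randomisation because residents are linked "by shared exposure to contagious illness, as occurs in nursing homes". Outbreaks, staffing and coding can also move one home and not another. The main analysis is unadjusted, so case-mix drift enters it too. The later adjusted models (age, gender, comorbidities, functional status) could absorb some of that drift, but they are not the main analysis.

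If true changes differ between homes, the interval for β3 is too narrow and a false claim of benefit is more likely than the plan allows. This is the trial's only success test.

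**Working it through.** **Inputs from the documents.** There are 28 homes, 14 per arm. The primary effect is 21.3% to 18.1% (a 15% relative reduction) with stated power 89% (95% CI 83% to 93%) from 200 resamples. For the all-cause outcome, 37.8% is reduced by 5% with stated power 74%.

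**Not in the documents.** The number of transfers is back-solved below. The SD of home-specific drift is taken as a range. Here s is the SD of a home-by-period effect on the log-odds scale, so the SD of a home's change is √2·s.

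**1. The plan's own figures.** Exact binomial limits for 178/200 are 83.8% to 93.0%, which agrees with the stated interval. The log-odds effect is logit(0.213) − logit(0.18105) = 0.2023. With binomial error only, 89% power implies

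SE(β3) = 0.2023/(1.960 + 1.227) = 0.0635 (0.059 to 0.069 over the stated power interval).

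Setting SE² = [3/(p0q0) + 1/(p1q1)]/n gives n of about 6,113 transfers per arm-period, or 437 per home-period.

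**2. True variance with drift.** For equal home sizes, Var(β3) = SE² + 4s²/14. The written model still uses SE², so its two-sided type I error is 2Φ(−1.96·SE/√Var). At s = 0.10, √(0.0635² + 4 × 0.01/14) = 0.0830, and 2Φ(−1.96 × 0.0635/0.0830) = 13.4%.

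| s | SD of change (√2·s) | Type I, formula | Simulated, equal sizes | Simulated, unequal sizes |
|---|---|---|---|---|
| 0 | 0 | 5.0% | 4.8% | 4.6% |
| 0.03 | 0.042 | 5.7% | 5.6% | 5.9% |
| 0.05 | 0.071 | 7.1% | 6.7% | 8.3% |
| 0.10 | 0.141 | 13.4% | 14.0% | 15.4% |
| 0.15 | 0.212 | 22% | 22.9% | 25.3% |
| 0.20 | 0.283 | 32% | 33.4% | 35.4% |

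The simulations fit the written random-intercept model to null data with an assumed intercept SD of 0.3. The equal-size column has 5,000 replicates per row (Monte Carlo SE 0.3 to 0.7 points). The unequal sizes have an assumed coefficient of variation of 0.4. With equal sizes the model's SE stayed at 0.063 while the actual SD of β3 was 0.063, 0.068, 0.083 and 0.125 at s = 0, 0.05, 0.10 and 0.20. A home-level t test on 26 df, on the same equal-size data, rejected 4.7% to 5.0%.

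The formula passes 10% at s of about 0.077. On the probability scale that is an SD of a home's true change of √2 × 0.077 × 0.213 × 0.787 = 0.018, or 1.8 percentage points. Over the range of SE in step 1, the figure at s = 0.10 runs from 12% to 15%.

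**3. All-cause outcome.** The stated 74% power gives SE = 0.0812/(1.960 + 0.643) = 0.0312. Type I error is then about 14%, 32% and 48% at s = 0.05, 0.10 and 0.15 (simulated 12.8%, 31.7% and 46.7%). It passes 10% at s of about 0.038. This outcome is more sensitive because its denominators are larger.

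**4. Power of a valid home-level test for 21.3% to 18.1%** (noncentral t, variance from step 2):

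| s | 26 df | 13 df |
|---|---|---|
| 0 | 87% | 84% |
| 0.05 | 81% | 78% |
| 0.10 | 65% | 62% |

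On 26 df, power falls below 80% once s exceeds about 0.053. The 13 df column is a pair-difference test with no credit for any gain from pairing.

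**5. Can the plan's resampling detect this?** Simulating its procedure on preliminary data generated with s = 0, 0.10 and 0.20 returned 89.7%, 89.1% and 90.4% power, and 5.6%, 4.8% and 5.7% rejection with no effect. Both periods come from the same home's data, so drift is zero by construction. The plan's claim that it need not guess the intra-class correlation covers differences between homes in level, not in change.

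**The case against.** The strongest objection is that the size rests on a number the documents do not give. The test is valid at s = 0, and at s of 0.03 or less the primary outcome's type I error stays under 6%. Short outbreaks partly average out over 18 months, and the remark on contagion was made to justify cluster randomisation, not to describe drift. This stands as a limit on the size.

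The transfer count is also inferred. At 170 transfers per home-period, simulated type I error is lower: 7.0%, 9.9% and 20.2% when the SD of change is 0.1, 0.2 and 0.3. However, the written model's simulated power at that volume and zero drift is only 52%, which does not fit the stated 89%.

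Benefit also requires a negative coefficient, so the rate of false claims of benefit is half the two-sided figure: at s = 0.10, 13.4%/2 = 6.7% against a nominal 2.5%. The relative inflation is unchanged.

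The equation is called a simple version and the text says random effects in the plural, so a richer model may have been intended. None is specified, and the only role the text gives those effects is to let baseline rates differ.

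Finally, the last plan is dated 8/10/2019, after the intervention ended ("18-month intervention period: July 2017-December 2018"), so new power figures cannot change the design. That is true, but they still bear on how a null result is read, and the analysis model remains open to correction.

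**Conclusion.** The concern holds. The written model has no home-by-period component, the success test therefore takes home-specific change as constant within arm, and the stated 89% power rests on the same assumption. These three points follow from the text.

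The size is conditional on s. Inflation is negligible for the primary outcome at s of 0.03 or less. Two-sided type I error is about 7% at 0.05, 13% at 0.10 and 32% at 0.20, and higher at the same s for the all-cause outcome. These figures rest on the transfer volume implied by the stated power and, for the formulas, on equal home sizes; the unequal sizes simulated gave somewhat more inflation at every s above zero. The plan neither estimates s nor protects against it. This must be fixed because it affects the sole test of trial success.

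**What to change.** Add a nursing-home-by-period random effect, or a random period slope per home, to the primary and secondary models. Test β3 with a small-sample degrees-of-freedom method that matches the randomisation actually used. Alternatively, use a permutation test that re-randomises homes exactly as the trial did.

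State the randomisation scheme in the final plan. It says only "Participating nursing homes (28) were randomized to" the two arms, and the amendment log records that the randomisation details were removed. The original plan discusses a scheme to "establish pairs with similar covariate profiles in which one member per pair is assigned to each arm". If homes were randomised unpaired, about 26 df applies; for a pair-difference test, about 13.

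Rerun the power resampling with a home-by-period component over a range of s. An estimate from preliminary or baseline data split by time within home would help, but it will be imprecise. With about 218 transfers per home-half, the sampling variance of a home's change is about 2/(218 × 0.168) = 0.055. At s = 0.10 the true variance of change is 0.020, and its estimate has a standard error of about (0.055 + 0.020) × √(2/27) = 0.020. Hence the range rather than a single value.

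**Cost.** The model change is small. With 26 df, the interval is about 1.05 times as wide as the written one at s = 0, 1.14 times at 0.05 and 1.37 times at 0.10. Power goes from the stated 89% to about 87%, 81% and 65%.

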## Nursing Protocol

### Nasal Antiseptic (10% Povidone-Iodine)

#### Who should receive iodophor?

- Adult residents in nursing homes participating in the PROTECT Trial
- Use on admission twice daily for 5 days and then twice daily for 5 days according to the nursing home's every other week schedule until discharge
- Do not use if the resident has an allergy to iodine
- If a resident is readmitted to the nursing home, the protocol starts again, including the admission treatment

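### The primary outcome counts transfers but the model indexes residents, and nothing accounts for repeat transfers by one resident

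*Combined protocol and SAP*

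**What the plan says.** The equation is the same in the 2015 and 2019 SAPs (Statistical Analysis). The index i is a nursing home and j "is a resident within the nursing home". The response, however, is set to 1 "if the transfer has an infection diagnosis and 0 if not", which is a property of a transfer. On correlation the plan says only this: "Clustering within nursing home will be accounted for using random effects". The equation contains one such effect, the home intercept, and the model terms listed in the text include none for the resident. The plan introduces the equation with "We can write a simple version of the model symbolically as".

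The 2015 design table defines the primary outcome as the share of hospital transfers that were for infection, and the Power section's 21.3% has the same denominator. The Trial Outcomes table of the 2019 SAP asks: "If the resident was transferred from the nursing home to a hospital, was the transfer made because the patient had an infection". Neither SAP restricts the analysis to one transfer per resident.

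The Nursing Protocol for iodophor provides for return stays: "If a resident is readmitted to the nursing home, the protocol starts again, including the admission treatment". Baseline and intervention periods each last 18 months.

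The Power section says that "individuals were sampled with replacement from within each nursing home", once for each period, and that the planned analysis was then run. It does not define an individual.

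**The concern.** A resident with two transfers, one for infection and one not, has no defined response under a home-and-resident index. Whoever builds the analysis file must therefore choose between one row per transfer and one row per resident. The denominator points to one row per transfer. In that case several rows can come from the same person, and whatever made one of that person's transfers infectious is likely to persist to the next. The written model treats those rows as independent once the home is known.

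The trial's conclusion rests on one two-sided 5% test of the interaction. If its standard error is wrong, so are the p-value and the confidence interval. The plan says all outcomes are assessed similarly, so the gap carries over to the secondary outcome, whose denominator is also a count of events.

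**Working it through.** **Inputs from the documents:** 28 homes, 14 per arm; two-sided alpha 0.05; 21.3% falling to 18.1% (15% relative reduction, 0.213 × 0.85 = 0.18105); power 89% (83% to 93%) from 200 simulations. **Not given:** numbers of transfers or residents, transfers per resident, within-resident correlation, share of residents contributing to both periods.

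**1. The plan's own figure.** The 89% cannot be recomputed without the preliminary data. Its interval can be: the exact interval for 178/200 is 83.8% to 93.0%, which matches the stated one apart from truncation. To see the implied scale, treat transfers as independent and let home effects cancel:

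- log odds ratio: ln(0.18105/0.81895) − ln(0.213/0.787) = −0.2023
- variance factor: 3/(0.213 × 0.787) + 1/(0.18105 × 0.81895) = 24.64
- transfers per arm and period: 24.64 × [(1.960 + 1.2265)/0.2023]² ≈ 6,100, or about 437 per home and period.

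**2. Repeats within a period.** Let M be transfers per resident per period, with mean m, and let ρ be the within-resident correlation. Variance is inflated by D = 1 + (E[M²]/E[M] − 1)ρ. With M taken as 1 + Poisson(m − 1), the bracket is 0.367, 0.833 and 1.5 for m = 1.2, 1.5 and 2.0. Then:

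- type I error of the planned test = 2Φ(−1.960/√D)
- valid power if transfer records were resampled (89% obtained under independence) = Φ(3.1865/√D − 1.960)
- valid power if whole residents were resampled (89% is then the rejection rate of the uncorrected test) = Φ(1.960/√D + 1.2265 − 1.960).

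With no resident in both periods:

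| m | ρ | D | Type I error | Valid power, records | Valid power, residents |
|---|---|---|---|---|---|
| 1.2 | 0.05 | 1.018 | 5.2% | 88.4% | 88.7% |
| 1.2 | 0.1 | 1.037 | 5.4% | 87.9% | 88.3% |
| 1.5 | 0.1 | 1.083 | 6.0% | 86.5% | 87.5% |
| 1.5 | 0.2 | 1.167 | 7.0% | 83.9% | 86.0% |
| 2.0 | 0.2 | 1.30 | 8.6% | 79.8% | 83.8% |
| 2.0 | 0.3 | 1.45 | 10.4% | 75.4% | 81.4% |

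A valid confidence interval would be wider by √D − 1, that is 1% to 20%.

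**3. Residents in both periods.** Their two sets of transfers are positively correlated, and this covariance cancels in the period contrast. If a share c of residents contributes to both periods, D becomes 1 + (E[M²]/E[M] − 1)ρ − c·m·ρ. The inflation vanishes at c = (E[M²]/E[M] − 1)/m:

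- m = 1.2: 0.367/1.2 = 31%
- m = 1.5: 0.833/1.5 = 56%
- m = 2.0: 1.5/2.0 = 75%.

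If M is geometric the bracket is 2m − 2, and break-even is 33% at m = 1.2 and 67% at m = 1.5. Above break-even the planned interval is too wide.

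**4. Simulation check.** I simulated 28 homes with 437 transfers per home and period, using home fixed effects in place of the random intercept, no treatment effect and 800 replicates. The ratios of true to model standard error (Monte Carlo error about 0.025) were:

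- m = 1.5, ρ = 0.2, no overlap: 1.07 (formula √1.167 = 1.08)
- the same with 30% overlap: 1.02 (formula √1.077 = 1.04)
- m = 1.2, ρ = 0.2, 50% overlap: 0.95 (formula √0.953 = 0.98).

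The case m = 2.0, ρ = 0.2, no overlap gave 1.07 against a formula value of 1.14. A longer run of 4,000 replicates gave 1.13 and a rejection rate of 8.6%, so the formula stands.

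**The case against.** The strongest reply is that nothing says every transfer enters as its own row. An index that stops at the resident, and an outcome question asked about the resident, both fit one record per person, and the equation is called a simplified version. This stands as far as it goes: analysis of all transfers is inferred from the denominator. But if one transfer per resident was meant, the SAP must say so and say which one. The simplified label does not help, because the listed terms and the model in the Power section contain no resident effect either. The facility transfer log is not evidence on either side, since the 2019 SAP takes the trial outcomes from electronic sources.

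A reader might infer that the main test certainly exceeds 5%. The documents do not support that. They give no overlap between periods, and overlap works in the opposite direction.

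A reader might also infer that the 89% is simply wrong, or that a particular lower figure replaces it. That does not follow either. If whole residents were drawn, within-period correlation is already in the simulated data, and 89% is a correct rejection rate for the planned test, though that test would then be anti-conservative. Several of the powers in the table also lie inside the plan's own 83% to 93% interval.

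Finally, a resident random intercept would make the odds ratio conditional on the resident, so it changes what is estimated. That objection is sound and shapes the fix.

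**Conclusion.** The mismatch between a per-transfer outcome and a per-resident index is in the text, and no term or variance estimator handles repeat transfers. If all transfers are analysed, the interaction's standard error is misstated. It is likely to be too small unless many residents have transfers in both periods, across a four-month gap; in that case it could be too large.

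For m from 1.2 to 2.0, ρ from 0.05 to 0.3 and no overlap, type I error is about 5% to 10%. Valid power is about 75% to 88% under record resampling and 81% to 88% under resident resampling. These ranges rest on assumed values and on the chosen count distribution. They show that the issue can matter; they do not estimate how much it does. The defect should be corrected, and either direction of error has the same remedy.

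**What to change.** 1. Write the response as R_ijk, for transfer k of resident j in home i, and state that all transfers are analysed. If only one per resident is intended, say which.
2. Keep the home-intercept model, but base the test and interval for the interaction on home-level cluster-robust standard errors with a small-sample correction for 28 homes. This covers repeats within and across periods without having to model them.
3. Offer a resident random intercept, nested in home and shared across periods, as a sensitivity analysis only, labelled as giving a resident-conditional odds ratio.
4. State whether the power simulation drew residents with all their transfers or single transfer records. Rerun it by resident with the corrected test and restate the power. The two periods were drawn separately, so neither reading reproduces residents who contribute to both; the rerun should state its assumption on overlap.
5. Apply the same rule to the secondary outcome.

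The cost is SAP wording, a change of variance estimator and a rerun of the simulation. The stated power will probably be slightly less favourable.
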